7.8.2 Laboratory data

Table and figure of eGFR (measurement value and change from baseline) by week will be created. Use age at baseline for calculation

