6.2 DETAILS OF STUDY PROCEDURES AT SELECTED VISITS

6.2.1 Screening and run-in periods

Before administration

The investigator will enter the following data of the patient into eCRF for registration. Preferably, registration should be executed within 14 days from the day of first administration of Trazenta® Tablets.

- Name of site, department and Investigator
- Patient ID, date of birth, gender, treatment group, start date of administration, indication, serum creatinine

The observation items are followings:

- Gender, date of birth, indication, pregnancy status, patient status (inpatient/outpatient), height, body weight, waist circumference, hypersensitivity factor, concomitant disease and medical history, pre-treatment drug, duration of type 2 diabetes mellitus, smoking status, start date of administration
- Concomitant drugs and antidiabetic therapy
- Measurement of vital signs (blood pressure, pulse rate and ECG) as safety measurement (if applicable)
- HbA1c , Fasting plasma glucose
- Laboratory tests (blood, biochemistry and urinalysis) (if applicable)

Haematology

- Leukocyte counts (WBC)
- Erythrocyte count (RBC)
- Platelet count

Blood chemistry

- AST (aspartate transaminase, SGOT)
- ALT (alanine transaminase, SGPT)
- γ-GTP (gamma-glutamyl-

- Haemoglobin (Hb)
- Haematocrit (Hct)
- HDL cholesterol (HDL)
- LDL cholesterol (LDL)
- Triglycerides (TG)
- Blood urea nitrogen (BUN)
- Amylase (AMY)

U13-1769-01

Proprietary confidential information © 2013 Boehringer Ingelheim International GmbH or one or more of its affiliated companies

Observational plan

transferase)

- Total bilirubin (T-BIL)
- Alkaline phosphatase (ALP)
- Lactic dehydrogenase (LDH)
- CK (creatine kinase)
- Total cholesterol (T-CHO)
- Lipase (LIP)
- Creatinine (CRE)
- Uric acid (UA)
- Sodium (Na)
- Potassium (K)
- Chlorine(Cl)

Urinalysis

1218.147

- Protein
- Glucose
- Urobilinogen

- Sediment
- Albumin
- Creatinine

eGFR

eGFR (mL/min/1.73 m²) =
$$194 \times$$
 Creatinine (mg/dL) $^{-1.094} \times$ Age $^{-0.287}$ For female, $\times 0.739$

6.2.2 **Treatment periods**

12 weeks, 26 weeks, 40 weeks, 52 weeks, 64weeks, 78 weeks, 104 weeks, 130 weeks, 156 weeks

The observation items are followings:

- Administration (compliance and fasting condition: 26, 78, 156 weeks)
- Concomitant drugs and antidiabetic therapy
- Adverse event
- Body weight
- Measurement of vital signs (blood pressure, pulse rate and ECG) (if applicable)
- HbA1c, Fasting plasma glucose

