7.2 NULL AND ALTERNATIVE HYPOTHESES

The analyses in this PMS are descriptive and exploratory by nature. Any statistical tests will be performed to provide a framework from which to view the results. No formal statistical inference will be made.

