7.3 PLANNED ANALYSES

The safety and efficacy analyses are applied only on Trazenta [®] Tablets.

The safety evaluation will be performed on the "safety set" that will include all patients who have received treatment of Trazenta[®] Tablets except those who are found to have no observation after enrolment, invalid registration, or invalid contract. The efficacy evaluation will be performed on the "efficacy set", a subset of the safety set, which will include all patients in the "safety set" except those who have no available efficacy data and/or who do not suffer from type 2 diabetes mellitus from the safety set.

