5.4 OTHER VARIABLE(S)

Demographic and baseline characteristics

- Sex (Male, Female)
- Age [years]
 - Actual age based on first administration of Trazenta®
- Age categories 1: \leq 50 years, 51 to 64 years, 65 to 74 years, \geq 75 years
- Age categories 2: <65 years, >65 years
- Height [cm]
- Body weight [kg]
- Body weight categories: \leq 50 kg, >50 to 70 kg, >70 to 90 kg, >90 kg
- Body mass index (BMI) [kg/m²]
 BMI [kg/m²] = weight [kg] / (height [m])²
- BMI categories 1: $<25 \text{ kg/m}^2$, 25 to $<30 \text{ kg/m}^2$, $\ge 30 \text{ kg/m}^2$
- BMI categories 2: $<25 \text{ kg/m}^2$, $\ge 25 \text{ kg/m}^2$
- BMI categories 3: $<30 \text{ kg/m}^2$, $\ge 30 \text{ kg/m}^2$
- Waist circumference [cm]
- Renal dysfunction: estimated glomerular filtration rate (eGFR) [mL/min/1.73m²]
- eGFR categories 1: ≥90 mL/min/1.73m²(Normal), 60 to <90 mL/min/1.73m²(Mild), 30 to <60 mL/min/1.73m²(Moderate), 15 to <30 mL/min/1.73m²(Severe), <15 mL/min/1.73m² (Endstage)

- eGFR categories 2: >60 mL/min/1.73m², <60 mL/min/1.73m²
- Hepatic dysfunction categories 1: (>ULN [35 U/L] of AST, >ULN of ALT [35 U/L], >ULN of total bilirubin [17 umol/L], or >ULN of ALP [120 U/L]), or other

In case > ULN of AST and CK increase (>400 U/L), patients do not include in hepatic dysfunction.

Conversion factors:

For total bilirubin: $17.102787754404 \times [mg/dL] = [umol/L]$ For AST, ALT, ALP: [IU/L] = [U/L]

Hepatic dysfunction categories 2: $\leq 1*ULN$, $\geq 1*ULN$ to $\leq 2*ULN$, $\geq 2*ULN$ to \leq 3*ULN, >3*ULN

Note: worst value of AST, ALT, total bilirubin, or ALP will be used for the categorization

- Hepatic dysfunction categories 3: (Yes, No, Unknown)
 - Hepatic disorders (Narrow) (SMQ 20000005)
 - Biliary disorders (Narrow) (SMQ 20000118) Note: Presence at baseline is yes
- Patient status: (In patient, Out patient)
- Indication (Type II diabetes mellitus, Other)
- Smoking status (Never, Ex-smoker, Smoker, Unknown)
- Duration of diabetes (≤1 years, >1 to 5 years, >5 years, Unknown) [First administration of Trazenta® (or other oral antidiabetic drug) – first diagnosis of type 2 diabetes mellitus + 1 (if negative value due to the missing and imputation, then 1)] / 365.25
- Hypersensitivity factor (Yes, No, Unknown)
- Concomitant diagnosis (Yes, No, Unknown)
- Cardiovascular (SMQ) history (Yes, No, Unknown)
 - Ischemic heart disease (SMO: 20000043)
 - Cardiac failure (SMQ: 20000004)
 - Cerebrovascular disorders (SMQ: 20000060)

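### Does holding age at baseline in the by-week eGFR table bias the renal follow-up results?

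*SAP*

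**What the plan says.** SAP section 7.8.2 is short. It states that "Table and figure of eGFR (measurement value and change from baseline) by week will be created", and then "Use age at baseline for calculation".

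Protocol section 6.2.1 gives the eGFR formula: 194 times creatinine to the power -1.094 times age to the power -0.287, with a factor of 0.739 for women. It does not say whether age is updated at follow-up visits. SAP section 5.4 defines age as "Actual age based on first administration of Trazenta", the same age that section 7.8.2 uses.

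The setting is single-arm and descriptive. Protocol section 7.3 says "The safety and efficacy analyses are applied only on Trazenta", and section 7.2 says "No formal statistical inference will be made".

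**The concern.** The age exponent is negative, so entering a younger age than the patient has reached gives a higher eGFR. If age stays at its baseline value for 156 weeks, follow-up values lie above the attained-age ones, always in the same direction and by more at later visits. Read that way, a decline in renal function would look smaller than it is and a rise larger.

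Three features make this look worth pursuing. There is no comparator arm in which the same shift would occur and cancel. Patients with renal dysfunction are a group that the authority asked the sponsor to include (Protocol section 7.6), and eGFR is the only laboratory parameter with a planned by-week output. Updating age would also be feasible, because the registration data include "Patient ID, date of birth, gender, treatment group, start date of administration, indication, serum creatinine". The SAP gives no reason for its choice. At stake would be a renal trend that looks better than the data warrant.

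**Working it through.** The plan states no figure for this effect, so there is none to reproduce. The inputs are the exponents in Protocol section 6.2.1 and the planned days in SAP Table 6.7: 1 (364, 728 and 1092). Baseline ages and eGFR levels are assumed, because the documents give no age distribution for this cohort. Age is treated as continuous.

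**Ratio of the two versions.** Creatinine and the sex factor are the same in both and cancel. For baseline age a and follow-up t in years:

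fixed-age eGFR / attained-age eGFR = ((a + t)/a)^0.287

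At week 156, t = 1092/365.25 = 2.99. For a = 65: (67.99/65)^0.287 = 1.0130, so the fixed-age value is 1.30% higher. The same formula gives:

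| Baseline age | Week 52 | Week 104 | Week 156 |
|---|---|---|---|
| 40 | 0.71% | 1.41% | 2.09% |
| 65 | 0.44% | 0.87% | 1.30% |
| 75 | 0.38% | 0.76% | 1.13% |
| 85 | 0.34% | 0.67% | 1.00% |

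**Absolute size.** At age 65 and week 156, 1.30% of an attained-age eGFR of 70, 60, 30 and 15 is 0.9, 0.8, 0.4 and 0.2 mL/min/1.73m². The baseline value is the same under both rules, so the change from baseline shifts by the same absolute amount. The percentage refers to the eGFR level, not to the change.

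**Unchanged creatinine.** Start at 70 at age 65 and leave creatinine as it was.
- Fixed age: 70 at week 156, change 0.0.
- Attained age: 70/1.0130 = 69.1, change -0.9.

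The only quantity measured again has not moved. The whole -0.9 comes from the age term.

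**A slow decline.** Suppose the attained-age value falls from 70 to 68.5 over three years, an assumed 0.5 per year. The three-year ratio is (68/65)^0.287 = 1.0130, so the fixed-age value is 68.5 × 1.0130 = 69.39, a change of -0.61 against -1.50. The difference of 0.89 is 60% of the attained-age fall. At an assumed 5 per year (70 to 55), the fixed-age value is 55.72, a change of -14.28 against -15, and the difference is 5%. These shares are the part of the attained-age fall that the age term supplies without any contribution from creatinine. They measure a missed decline only if that part counts as loss of renal function observed in this study.

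**What the rule touches.** At t = 0 the ratio is 1, so baseline eGFR, the eGFR categories in SAP section 5.4 and the renal recruitment targets in Protocol section 3.3 are the same under either rule. The safety endpoints in Protocol section 5.2.1 are incidences of adverse drug reactions and serious adverse events, and the secondary endpoint is HbA1c. None uses follow-up eGFR.

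**The case for a change.** The best argument for the concern is that fixing age can justify the change column but not the value column. A week-156 value computed with baseline age is not what the formula returns for that patient on that date, and the SAP does not say why it is shown.

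The first part is true as a description, and at age 65 the difference is the 0.2 to 0.9 mL/min/1.73m² shown above. But value and change appear in one output. If the values used attained age and the changes used fixed age, the change would no longer equal the follow-up value minus the baseline value. One age rule for both keeps the table coherent.

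The lack of a comparator works in both directions. No control arm removes the fixed-age shift. Equally, no control arm would separate the decline built into attained age from an effect of the drug. In a single-arm safety table, that is a reason to prefer fixed age.

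What stands is that the SAP gives no rationale and no footnote text. That is missing detail: the rule itself is in the SAP for any reader, and the absence of a footnote there does not show that the output will be unlabelled.

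**Conclusion.** The concern does not hold. The direction and the arithmetic are right: fixed-age eGFR exceeds attained-age eGFR by about 1% to 2% of its level at week 156 for baseline ages 40 to 85. This does not make the plan wrong. The rule was stated in advance, agrees with SAP section 5.4 and contradicts nothing in Protocol section 6.2.1. Calling the difference a bias requires treating the attained-age figure as the truth, and nothing in the documents does so. Which age to use is a trade-off between an eGFR at current age and a change driven only by what was measured again. Statisticians may reasonably differ on it.

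The consequence is also small. The output is one descriptive table and figure, based on laboratory tests done at the investigator's discretion (Protocol section 5.2.3). In the severe and end-stage range the shift is about 0.2 to 0.4 mL/min/1.73m² at age 65. No endpoint, analysis set, baseline category or planned conclusion depends on it. The sizes rest on assumed ages and eGFR levels; the assessment of the rule does not depend on them.

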7.8.3 Vital signs

Table and figure of blood pressure and weight (measurement value and change from baseline) by week will be created.

7.8.4 ECG

Only clinically relevant findings reported as AE will be analysed as a part of AE analyses.

7.8.5 Others

No plan for other safety parameters.

10. HISTORY TABLE

Table 10: 1 History table

Version	Date	Author	Sections	Brief description of change
	(DD-Mmm-YY)		changed	
Final	12-Oct-18		None	This is the final TSAP without any
				modification
